The most common product-related AE observed in clinical studies with AAV-mediated gene transfer to subjects with moderate to severe hemophilia B has been an asymptomatic transient rise in liver aminotransferases (still within the normal reference range for these laboratory parameters) and concurrent decline in transgene expression approximately 7 to 10 weeks following vector administration [Manno 2006; Nathwani 2011a; Nathwani 2014]. In all cases, the transient rise in liver aminotransferases resolved without clinical sequelae. It has been hypothesized that this vector-induced hepatitis is due to the activation of capsid-specific cytotoxic T lymphocytes and destruction of transduced liver cells [Mingozzi 2007]. As this is the only identified AE with AAV gene transfer and, given that subjects in this study will be closely monitored for vector-induced hepatitis and treated with corticosteroids (Section 8.2.4.1.2), having an interval of more than 14 days between subjects within Cohorts 1 and 2 and 7 days between the first 3 subjects in Cohort 3 does not change either safety evaluations or the medical management of study subjects. To date, no infusion-related or serious AEs (SAEs) have been reported with DTX301. Aligned with previous experience [Manno 2006; Nathwani 2011a; Nathwani 2014], only mild, transient, asymptomatic rises in liver enzymes have been observed in 6 subjects starting approximately 8 days to 7 weeks after vector administration that resolved with an oral corticosteroid taper regimen [Diaz 2019; Ultragenyx Pharmaceutical, data on file;]. To allow for refinement in management of asymptomatic transient rises in liver aminotransferases (vector-induced hepatitis) and concurrent decline in transgene expression following AAV vector administration, Cohort 4 (Dosing Process Optimization) will utilize an alternative regimen of oral corticosteroids. Based on available evidence, it is expected that vector-induced hepatitis will be self-limiting. Therefore, oral prednisone (or prednisolone) will be employed in a prophylactic regimen initiated before dosing with DTX301, sustained for 4 weeks, followed by tapering (Section 8.2.4.1.2). Prophylactic corticosteroid regimens are in use for gene transfer therapies [Audentes 2017 Clinicaltrials.gov identifier: NCT03223194; Abeona Therapeutics 2016 ClinicalTrials.gov identifier: NCT02716246].

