8.2.4.1.2 Treatment for Possible Vector-Induced Hepatitis

The investigator, in conjunction with the Ultragenyx Pharmaceutical Inc. medical lead will consider starting oral steroid treatment, per protocol, for possible vector-induced hepatitis when a subject's **ALT is greater than the ULN** and is considered by the investigator to be related to treatment with DTX301. The subject must be assessed as clinically and metabolically stable, and intercurrent illnesses (eg, viral infection) or concomitant medications known to affect transaminases, be excluded.

Repeat liver function testing for confirmation of results should be considered to inform the use of steroid treatment. If repeat testing is deemed necessary, every effort should be made to repeat the testing within 24 hours from receipt of test results indicating elevated ALT.

At any point between scheduled visits, additional, unscheduled assessment for LFTs, plasma ammonia, or any other biomarker to assess subject safety and clinical status may be performed, at the discretion of the investigator.

Changes to baseline treatment (ie, ammonia scavenger medications and protein-restricted diet) cannot occur while the subject is treated with corticosteroids or within a 2-week period of completing a corticosteroid taper.

Based on available evidence, it is expected that vector-induced hepatitis will be self-limiting. Therefore, oral prednisone (or prednisolone) will be used per the American Association for the Study of Liver Disease guidelines, with a slight modification in **Cohorts 1 to 3**:

- Week 1: prednisone 60 mg/day
- Week 2: prednisone 40 mg/day
- Week 3 and Week 4: prednisone 30 mg/day
- Week 5 and thereafter: prednisone will be tapered by 5 mg/week until liver enzymes return to baseline levels. The use of prednisone will be recorded on the appropriate page in the eCRF.

Protocol: 301OTC01

Cohort 4 (Dosing Process Optimization) will utilize an alternative regimen of corticosteroids, aiming at prophylaxis of vector-induced hepatitis. Therefore, oral prednisone (or prednisolone) will be initiated before dosing with DTX301, sustained for 4 weeks, followed by tapering as described below. Prophylactic corticosteroid regimens are in use for gene transfer therapies [Audentes 2017 Clinicaltrials.gov identifier: NCT03223194; Abeona Therapeutics 2016 ClinicalTrials.gov identifier: NCT02716246].

- At least 5 days prior to dosing: prednisone 60 mg/day

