- An additional clinical trial (ClinicalTrials.gov identifier: NCT02716246) was referenced as justification for the prophylactic steroid regimen to be introduced in Cohort 4 (Dosing Process Optimization; Sections 1.3.1, 8.2.4.1.2).
- The definition of baseline for the rate of ureagenesis was removed globally with the intent that baseline definitions will be presented in the statistical analysis plan (Sections 2, 10.5.2.1).
- The text, "in the setting of tapering or discontinuing ammonia scavenger medications," was removed from exploratory endpoints 2 and 3 (ie, urinary orotic acid excretion and glutamine and glutamate). The change was made because the intent is to assess these endpoints in all subjects, regardless of baseline treatment status (Section 2).

Protocol: 301OTC01

- The specified timing, “weekly,” was removed from the exploratory endpoint that evaluates use of ammonia scavengers. This change was made to reflect the manner by which the data are being captured and reported and to reflect subject management, which requires daily intake of scavengers at a prescribed dose (Sections 2, 8.7.2, 10.4).
- The exploratory endpoints and corresponding assessments determined by the enzyme-linked immunospot [ELISPOT] assay and related to cell-mediated immune response to AAV8 and OTC were removed globally. These assays are exploratory in nature and to date have not revealed informative results, and require notable blood volume to be collected from subjects (Sections 2, 8.2, 8.2.4.1.1, 10.4, 10.5.3.6, Table 15-1).
- The sample size was updated from “approximately 6 to 18 subjects” to “up to 18 subjects” to reflect the current enrollment status of 9 subjects and plans to continue enrollment (Section 3.2).
- It was added that “where available, agreed upon by the investigator and allowed by local regulation, an outpatient clinic visit may take place as home health services.” The Week 20 visit remains a mandatory outpatient clinic visit. This change was made to allow increased flexibility for protocol-specified abbreviated visits that may be performed as home health visits and have the potential to reduce subject burden in certain situations (Sections 3.2, 3.2.3, 3.2.3.2, 12.4, Figure 3-1, Table 15-1).
- More comprehensive guidance and testing specifications were added to the rescreening procedure to ensure consistent testing and evaluations prior to enrollment and dosing (Section 3.2.1, Table 15-1).

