4.13. Subject Identification

Subjects will be identified in data listings by subject identification number which consists of the subject number concatenated with the site number. Data listings will be sorted by subject identification number, visit, and parameter (where applicable).

4.14. **Unscheduled Visits**

Unscheduled visits will not be included in by-visit summaries of data with the exception of worst post-baseline value in the shift from baseline summary of electrocardiogram (ECG) interpretation and summaries of worst post-baseline value for hematology, chemistry, urinalysis and amino-acid and summaries of newly notable laboratory abnormalities in chemistry relating to liver function test results. Moreover, unscheduled visits will be included into individual patient graphs.

4.15. **Analysis Sets**

4.15.1. **Safety Set**

The Safety Set (SS) will include all subjects who receive DTX301. Subjects who receive a partial dose will be summarized or listed according to the nearest candidate dose (see [Table 3-1](#)) based on the actual dose they received. The SS will be used to tabulate and list all of the safety endpoints, efficacy endpoints, and for the purpose of N-CRM modelling.

4.15.2. **MTD Determining Set**

See Section 3.2.8 for details.

5. **Subject Disposition**

5.1. **COVID-19**

[figure not shown]
At the onset of the Coronavirus Disease 2019 (COVID-19) pandemic in Europe and North America, only 2 subjects in cohort 3 were ongoing [REDACTED]. Due to the spacing of visits and number of ongoing subjects, it was decided to collect the impact of COVID-19 on the visits and/or assessments missed using a specific eCRF page and not to change the planned analysis. This data collection method was planned to be applied to patient [REDACTED] and, if applicable, to all patients of cohort 4 as well. All data collected on this page will be listed in a data listing.

Table 5–1 Pandemic Lock-down Restrictions Start/End Dates

| Country (region) | Lock-down Start Date | Lock-down Stop Date |
|-------------------------|-----------------------------|----------------------------|
| UK | 24-Mar-2020 | 15-Jun-2020 |
| | 05-Nov-2020 | 02-Dec-2020 |
| | 04-Jan-2021 | 12-Apr-2021 |
| Spain | 14-Mar-2020 | 11-May-2020 |
| France* | 17-Mar-2020 | 11-May-2020 |
| | 30-Oct-2020 | 14-Dec-2020 |
| Canada | 13-Mar-2020 | 04-May-2020 |

| | | |
|---------------------|-------------|-------------|
| USA (Massachusetts) | 24-Mar-2020 | 25-May-2020 |

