9.1. Adverse Events

An AE is defined as any untoward medical occurrence in a subject enrolled into this study (from the time the subject signs the ICF until their exit from the study) regardless of its causal relationship to study drug. A treatment-emergent adverse event (TEAE) is defined as any event not present before exposure to study drug, or any event already present that worsens in intensity (i.e. severity) or frequency after exposure to study drug. Any events which occur after exposure to study drug and before the first visit of the extension study (301OTC02) will also be considered as TEAEs.

AEs will be coded using MedDRA; the dictionary version used for reporting the study will be described in the relevant table and listing footnotes. Severity/toxicity grade will be defined according to the most current version of the National Cancer Institute Common Terminology Criteria for Adverse Events (NCI-CTCAE).

There are four categories of relationship collected on the eCRF: “Unrelated”, “Possible”, “Probable”, or “Definite”. A related AE is an event where the investigator determined that the relationship to study drug was “Possible”, “Probable”, or “Definite”. For summaries by relationship, AEs with a missing relationship will be considered to be “Possible”. TEAEs will be summarized by strongest relationship. The investigator will also indicate whether

the AE is related to [1-¹³C] sodium acetate, OTC deficiency, hyperammonemia, and as of protocol amendment 5, to corticosteroid regimen.

An HAC-related TEAE is defined as a TEAE which has been identified as associated with the crisis in the eCRF “Hyperammonemic Crisis” page.

If AE start date is missing, it will be imputed as described in the [Appendices](#).

The incidence and the number and percentage of subjects will be summarized by DTX301 dose/prophylactic corticosteroids and overall for each of the following:

- All TEAEs
- All serious TEAEs
- All TEAEs with grade ≥ 3
- All study drug related TEAEs
- All study drug related serious TEAEs
- All study drug related TEAEs \geq grade 3
- All TEAEs related to corticosteroid regimen (prednisone/prednisolone)
- All HAC-related TEAEs
- TEAEs leading to study discontinuation
- Any AE leading to death

The number and percentage of subjects with TEAEs will be summarized by DTX301 dose/prophylactic corticosteroids, overall, SOC, and PT for each of the following:

- TEAEs (including incidence)
- TEAEs by relationship (including incidence)

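### The by-cohort tables of corticosteroid-related TEAEs use the whole Safety Set, although the attribution was collected only from Amendment 5, and they omit the Cohort 4 steroid lead-in

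*SAP*

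**What the plan says.** SAP 9.1 first defines a related AE by its relationship to study drug. It then says of blanks: "For summaries by relationship, AEs with a missing relationship will be considered to be" Possible. Next it lists further attributions that the investigator makes, ending "hyperammonemia, and as of protocol amendment 5, to corticosteroid regimen". Protocol 15.3.5 confirms that steroid attribution was added at Amendment 5, at the DMC's request.

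The overview table, by cohort and overall, includes "All TEAEs related to corticosteroid regimen (prednisone/prednisolone"). A second table gives the same events by system organ class and preferred term. Percentages are taken over the analysis set. SAP section 9 makes that the Safety Set, and SAP 4.15.1 says: "The Safety Set (SS) will include all subjects who receive DTX301". Nothing in SAP 9.1 restricts these tables by period, adds a footnote, or says whether earlier AEs were attributed retrospectively.

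A TEAE is defined by exposure to study drug. In Cohort 4 the steroid comes first: "At least 5 days prior to dosing: prednisone 60 mg/day" (Protocol 8.2.4.1.2). In Cohorts 1 to 3 steroids are given after DTX301, in response to an ALT rise.

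**The concern.** The tables put a prophylactic-steroid cohort beside reactive-steroid cohorts, and the two are not captured alike.

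The attribution field did not exist for most of the follow-up in Cohorts 1 to 3, yet every subject in those cohorts stays in the denominator. A low percentage there could mean few steroid-related events, or only that nobody was asked. The SAP handles the reverse case: ELISPOT (8.3.6) and vector genome (9.4) outputs leave out subjects enrolled after Amendment 5 dropped those assessments. A field added at the same amendment gets no such treatment.

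The event window also starts too late for Cohort 4 and nowhere else, because only Cohort 4 has steroid exposure before DTX301.

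SAP 3.1 calls the performance of the prophylactic regimen the focus of Cohort 4, so its tolerability relative to reactive use is something a reader will look for in this table.

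**Working it through.** The documents give no percentage or sample-size figure for this table, so there is none to reproduce. The check is one of dates, counts and bounds.

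**Inputs**
- Field starts: Amendment 5, 25 February 2020 (SAP 9.1; Protocol 15.3.5).
- Enrolled at that point: 9. The sample size was revised "to reflect the current enrollment status of 9 subjects and plans to continue enrollment" (Protocol 15.3.5).
- Ongoing at pandemic onset: "only 2 subjects in cohort 3 were ongoing" (SAP 5.1). The earliest lockdown listed there is 13 March 2020, which is 17 days after the amendment date.
- Steroid-treated enzyme rises already reported: "only mild, transient, asymptomatic rises in liver enzymes have been observed in 6 subjects", with the text adding that they resolved on an oral steroid taper (Protocol 1.3.1).
- Cohort 4: 2 subjects (SAP 3.1). None was ongoing at pandemic onset, so both appear to have been followed wholly under Amendment 5.

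**Who can carry a prospectively recorded attribution**
- Cohorts 1 to 3, no longer ongoing: 9 − 2 = 7, and 7/9 = 78%.
- Cohorts 1 to 3, able to contribute: at most about 2/9 = 22%.
- Cohort 4: 2/2 = 100%.

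The 2/9 is generous. It treats both remaining Cohort 3 subjects as if they carried the field throughout, although part of their follow-up predates it.

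**Effect on the table.** Assume the same true proportion p of subjects with a steroid-related TEAE in every cohort, and no retrospective attribution. If blanks count as unrelated, the expected percentage shown for Cohorts 1 to 3 is 2p/9:

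| p (assumed) | Shown, Cohorts 1 to 3 | Expected, Cohort 4 |
|---|---|---|
| 0.2 | 4.4% | 20% |
| 0.4 | 8.9% | 40% |
| 0.6 | 13.3% | 60% |
| 0.8 | 17.8% | 80% |

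The true rates are equal in every row, so the gap comes only from when the field was added. If the missing-to-Possible rule were instead applied to this field, and each of the 7 earlier subjects had at least one TEAE (an assumption), the figure would be (7 + 2p)/9. That runs from 82% at p = 0.2 to 96% at p = 0.8.

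**Lead-in in Cohort 4.** The planned course is at least 5 days before DTX301, 28 days at the plateau, and six taper steps of 5 days (30 days). The total is 5 + 28 + 30 = 63 days, so the share before DTX301 is 5/63 = 7.9%. With an assumed lead-in of 7 to 14 days it is 7/65 = 10.8% to 14/72 = 19.4%. For reactive courses it is 0%. (Protocol 8.2.4.1.2 places the 30-day taper in Weeks 5 to 8, which is 28 days. Those statements need reconciling, but with 28 days the share is 5/61 = 8.2%, so the point is unaffected.)

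**The case against.** Several points on the other side are sound.

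- **Primary endpoint.** A reader might infer that the primary safety endpoint is compromised. It is not. That endpoint is AE, TEAE and SAE incidence by severity and relationship to study product, and steroid attribution plays no part in it.
- **Handling of blanks.** A reader might infer that the table could show anything from 0/9 to 9/9 for Cohorts 1 to 3. Neither end is supported. Two Cohort 3 subjects could carry the field, so zero is not forced. The missing-to-Possible sentence directly follows the definition of relatedness to study drug and comes before any mention of steroids, so its natural reading is DTX301 only. Protocol 9.1.4 does apply the same causality terms to the steroid regimen, so saying so explicitly is still worthwhile.
- **Retrospective completion.** The documents do not say that earlier AEs were left without a steroid attribution. If they were reviewed later, the first part of the point reduces to a missing statement.
- **Lead-in events.** These are not lost. SAP 9.1 lists all AEs, and separately AEs related to the corticosteroid regimen, for the Safety Set, and AEs are collected from consent. An event that worsens after DTX301 is also a TEAE. The loss is from the tables only.
- **Undosed subjects.** Someone who starts prednisone and is never dosed would fall outside the Safety Set, but nothing indicates that this happened.
- **Scale.** Safety analyses are descriptive and Cohort 4 has 2 subjects; the exact 95% interval for 0/2 is 0 to 84%. The regimen's main aim, limiting aminotransferase rises, is shown in the ALT tables and plots.

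These points limit the consequence. They do not remove the mismatch between a full Safety Set denominator and a field that began at Amendment 5.

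**Conclusion.** The point holds as a correctable flaw in a supporting, descriptive safety table. Under the stated rules, at most about 2/9 (22%) of Cohort 1 to 3 subjects can show a prospectively attributed event, against 2/2 in Cohort 4. The Cohort 4 count also leaves out events confined to a lead-in of at least 5 days. The direction of the net distortion is not fixed: late introduction of the field lowers Cohorts 1 to 3 if blanks count as unrelated, while the event window lowers Cohort 4.

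This rests on four assumptions. Earlier AEs were not attributed retrospectively. The 9 subjects enrolled at Amendment 5 were all in Cohorts 1 to 3. The 2 Cohort 3 subjects were the only ones ongoing at pandemic onset, with few completions in the 17 days before it. No Cohort 3 expansion subjects were added later; the documents report none. Site-level dates for implementing the amendment are not given, so the seven and two are approximate.

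**What to change.** In SAP 9.1:

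1. Base both steroid-related TEAE tables on the subjects and AEs for which the field was collected, and print that denominator. Mark the earlier Cohort 1 to 3 period as not collected. If attribution was completed retrospectively, state that and keep the full denominator.
2. State that missing-to-Possible applies to relationship to DTX301 only.
3. In the steroid-related table, count Cohort 4 events from the first prophylactic prednisone or prednisolone dose, and title the table so that this window is clear.

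Two additions are optional. One is a table of AEs with onset while on steroids. It avoids attribution but is not a clean comparison, because reactive courses are triggered by ALT rises and vary in length. The other is a listing of AEs for anyone who started prophylaxis and was not dosed.

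The cost is a few sentences of SAP text and minor programming on data already collected, with smaller denominators in Cohorts 1 to 3. No visits or subjects are added.

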9.2. Death

All subjects who have an AE with an outcome of death will be presented in a listing. Date of death, and death certificate completion status will be included.

9.3. Clinical Laboratory Evaluations

Summary tables presenting observed values and changes from baseline to each scheduled post-baseline time point and minimum/maximum post-baseline value will be provided for clinical chemistry, hematology, urinalysis, and amino acids using standardized results.

Results of clinical chemistry, hematology, and amino acid parameters will be categorized as low, normal, or high according to laboratory range specifications. Shifts from baseline to each scheduled post-baseline time point will be presented to show the number and percentage of subjects in each category by parameter.

Results of urinalysis parameters will be categorized as normal or abnormal. Shifts from baseline to each scheduled post-baseline time point will be presented to show the number and percentage of subjects in each category by parameter.

Spaghetti plots for both ALT and aspartate aminotransferase (AST) results separately, over time will be provided.

A box plot of ALT results before and after gene transfer will be provided.

Clinical Chemistry

- ALT, albumin, alkaline phosphatase (ALP), AST, bilirubin (total and indirect), blood urea nitrogen (BUN), calcium, carbon dioxide, chloride, creatine kinase, creatinine, gamma-glutamyl transferase (GGT), glucose, magnesium, lactate dehydrogenase (LDH), phosphate, potassium, sodium, and total protein

Hematology (including Coagulation Panel)

- activated partial thromboplastin time (aPTT), basophils, basophils/leukocytes, eosinophils, eosinophils/leukocytes, erythrocyte mean corpuscular hemoglobin (MCH), erythrocyte mean corpuscular hemoglobin concentration (MCHC), erythrocyte mean corpuscular volume (MCV), erythrocytes, hematocrit, hemoglobin, leukocytes, lymphocytes, lymphocytes/leukocytes, monocytes, monocytes/leukocytes, neutrophils, neutrophils/leukocytes, platelets, international normalized ratio (INR), prothrombin time.

Urinalysis

- blood, glucose, ketones, pH, protein, specific gravity, and microscopic examination (if blood or protein is found)

Amino Acid Panel

- Alanine, amino-butyric acid, arginine, asparagine, aspartic acid, , citrulline, cystine, ethanolamine, glutamic acid (aka “serum glutamate”), glutamine, glycine, histidine, homocysteine, hydroxyproline, isoleucine, leucine, lysine, methionine, ornithine, phenylalanine, proline, serine, taurine, threonine, tryptophan, tyrosine, and valine.

Clinical chemistry measurements will be processed by both PPD Global Central Laboratory and local laboratories (liver function tests only) and summarized separately. Hematology and urinalysis measurements will be processed only by PPD Global Central Laboratory and summaries related to these laboratory categories will be limited to central lab results.

Microscopic urinalysis results will be listed only. All laboratory data test results will be included by subject in applicable data listings.

Newly notable laboratory abnormalities (i.e. abnormal post-baseline test results with corresponding normal baseline test results for a given parameter) in clinical chemistry, hematology, and urinalysis will be flagged in corresponding data listings.

The number and percentage of subjects with ALT results greater than upper limit of normal (ULN) and also greater than or equal to $2.5 \times \text{ULN}$ using both local and central laboratory results will be summarized at each scheduled post-baseline time point and also corresponding to the maximum post-baseline value. If both central and local laboratory results are available for the same visit for a given subject, the highest result will be used for analysis purposes (regardless of the source).

